5.5.5 Permitted dose adjustments and interruptions of study treatment

For potential drug-related adverse events, temporary interruptions are permitted up to 28 consecutive days. Study drugs can be reintroduced under careful monitoring if the investigator feels it is in the best interest of the patient. Interruption of study drug for more than 28 consecutive days should lead to permanent discontinuation of the patient from study drug with the respective follow-up visits.

Investigational treatment dose adjustments are not permitted.

These changes must be recorded on the appropriate eCRF.

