The appropriate personnel from the study site and Novartis will assess whether study treatment should be discontinued for any patient whose treatment code has been broken inadvertently for any reason. Study treatment must be discontinued after emergency unblinding. If discontinuation of study treatment occurs, the patient should NOT be considered withdrawn from the study. The patient should return to the clinic as soon as possible, after discontinuation of study drug, for a study treatment discontinuation visit. Treatment discontinuation visit assessments detailed in the treatment discontinuation visit (TD) in [Table 6-1](#) should be completed and recorded in the appropriate eCRF. The investigator must determine the primary reason for the patient's premature discontinuation of study treatment and record this information on the appropriate eCRF. The investigator must also contact the IRT to register the patient's discontinuation from study treatment.

During the Treatment discontinuation visit (TD), at least the following data should be collected:

- new/concomitant treatments
- adverse events/Serious Adverse Events

For patients who discontinue study treatment prematurely before the end of the treatment period for any reason other than withdrawal of informed consent, the TD visit (EOT) and Week 52 (EOS) visits must be performed.

If study drug discontinuation occurs because treatment code has been broken, refer to protocol [Section 5.5.9](#).

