Any unplanned assessments for: Vital signs, ECG, Hepatitis serology, Liver tests, Serum BUN and Creatinine, Coagulation panel, [REDACTED] Clinical chemistry panel, HbA1c, Urinalysis and Serum pregnancy test must be recorded in the unplanned eCRF.

For patients who discontinue study treatment prematurely before the end of the treatment period for any reason other than withdrawal of informed consent, the Week 48, planned End of Treatment (EOT) and Week 52 End of Study (EOS) visits must be performed.

If a patient refuses to return for these assessments or is unable to do so, every effort should be made to contact them, or a knowledgeable informant, by telephone or by sending appropriate correspondence (i.e. certified letter) immediately. At this contact, the safety (e.g. potential occurrence of AEs or SAEs) and the primary reason for the patient's premature withdrawal should be determined. Documentation of attempts to contact the patient should be recorded in the patient source documents.

Refer to Section 5.6 for additional details regarding procedures for patients who discontinue study treatment or prematurely withdraw.

Patients will be contacted for safety evaluations during the 30 days following the last administration of study treatment.

[figure not shown]
Patients who develop medically important laboratory abnormalities or medically important adverse events (AE) that are considered related to study drug will be followed beyond the End of Study visit until these events have resolved or stabilized.

The following will be considered as medically important:

- i. severe AEs,
- ii. serious AEs,
- iii. hepatic and renal AEs,
- iv. elevated liver enzymes (ALT, AST or alkaline phosphatase >2x ULN and >1.5x baseline).

Table 6-1 Assessment schedule

[figure not shown]
Periods	Screening		Treatment Period										Post Treatment Follow Up	Notes
	-10 to -2	-2 ¹ (no later than) ²	BSL	2	4	8	12	16	24	32	40	48 ¹⁶ TD/EOT		
Screening														
Informed consent	X													
Pharmacogenetic informed consent	X													
Inclusion / Exclusion criteria	X	X	X											
Demography	X													
Medical history/ current medical conditions	X													
Protocol solicited medical history	X													
Assessments														
Physical examination ³	S	S	S		S	S	S	S	S	S	S	S	S	
Prior and concomitant medication	X	X	X	X	X	X	X	X	X	X	X	X	X	
Surgical and medical procedures	X	X	X	X	X	X	X	X	X	X	X	X	X	
Alcohol history / compliance with protocol	X	X	X	X	X	X	X	X	X	X	X	X	X	

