7.2.2 SAE reporting

To ensure patient safety, every SAE, regardless of causality, occurring after the patient has provided informed consent and until 30 days following the last administration of study treatment must be reported to Novartis safety within 24 hours of learning of its occurrence. Any SAEs experienced after the 30 day period after the last study visit should only be reported to Novartis safety if the investigator suspects a causal relationship to study treatment. For patients who sign the pre-screening informed consent form, SAEs which occur after signature of this consent will only be captured if they are reported to be causally related with study procedures (i.e. blood sampling).

All follow-up information for the SAE including information on complications, progression of the initial SAE and recurrent episodes must be reported as follow-up to the original episode within 24 hours of the investigator receiving the follow-up information. An SAE occurring at a different time interval or otherwise considered completely unrelated to a previously reported one must be reported separately as a new event.

Information about all SAEs is collected and recorded on the Serious Adverse Event Report Form; all applicable sections of the form must be completed in order to provide a clinically thorough report. The investigator must assess the relationship of each SAE to each specific component of study treatment, (if study treatment consists of several components) complete the SAE Report Form in English, and submit the completed form within 24 hours to Novartis. Detailed instructions regarding the submission process and requirements for signature are to be found in the investigator folder provided to each site.

Follow-up information is submitted as instructed in the investigator folder. Each re-occurrence, complication, or progression of the original event must be reported as a follow-up to that event regardless of when it occurs. The follow-up information should describe whether the event has resolved or continues, if and how it was treated, whether the blind was broken or not, and whether the patient continued or withdrew from study participation.

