9.5.2.1 Adverse events

Treatment emergent adverse events (events started after the first dose of study treatment or events present prior to the first dose of study treatment but increased in severity based on preferred term) will be summarized. AEs will be summarized by presenting, for each treatment group, the number and percentage of patients having experienced

- Any adverse event (AE),
- Any serious adverse event (SAE),
- Any adverse event by primary system organ class (SOC),
- Any adverse event by preferred term,
- Any adverse by severity,
- Any adverse event possibly related to study treatment (investigator assessment),
- Any adverse event resulting in discontinuation of study treatment,
- Any adverse events of special interest for tropifexor or CVC treatment.

Exposure adjusted tabulations of adverse events and tabulations of appropriate adverse events according to defined intervals will be provided as well. If a patient reported more than one adverse event with the same preferred term, the adverse event with the greatest severity will be presented. If a patient reported more than one adverse event within the same primary system organ class, the patient will be counted only once with the greatest severity at the system organ class level, where applicable. A separate summary will be provided for deaths, if they occur during the course of the study.

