### **2.5 Analysis of the primary objective**

#### **2.5.1 Primary endpoint**

The primary study objective is to evaluate the safety and tolerability of tropifexor + CVC in patients with NASH and fibrosis (stage 2 or 3 as per NASH CRN histological score, F2/F3) by monitoring adverse events, vital signs and laboratory values during treatment as compared to monotherapy with each of tropifexor and CVC. The related endpoints are (over treatment):

- occurrence of adverse events,
- occurrence of serious adverse events,
- occurrence of adverse events resulting in discontinuation of study treatment,

- occurrence of adverse events of special interest,
- changes in vital signs and laboratory values.

Only treatment emergent adverse events will be considered for the analysis, which are defined as those starting on or after first day of application of study treatment and before EOS visit or 30 days after EOT visit, whichever comes earlier.

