### 2.8.1 Adverse events (AEs)

Treatment emergent adverse events (events started after the first dose of study treatment or events present prior to the first dose of study treatment but increased in severity based on preferred term, until EOS visit or 30 days after EOT visit, whichever comes earlier) will be summarized. AEs will be summarized by presenting, for each treatment group, the number and percentage of patients having experienced

- Any adverse event (AE),
- Any serious adverse event (SAE),
- Any adverse event by primary system organ class (SOC),
- Any adverse event by preferred term (PT),
- Any adverse event by severity,
- Any adverse event possibly related to study treatment (investigator assessment),
- Any adverse event resulting in discontinuation of study treatment,
- Any adverse events of special interest for tropifexor or CVC treatment,
- Any adverse events by onset time before and after the start date of COVID-19 pandemic by country/region,
- Any serious adverse events by onset time before and after the start date of COVID-19 pandemic by country/region.

If a patient reported more than one adverse event with the same preferred term, the adverse event with the greatest severity will be presented. If a patient reported more than one adverse event within the same primary system organ class, the patient will be counted only once with the greatest severity at the system organ class level, where applicable.

The start date of COVID-19 for different countries or regions is defined in Table 5-1 of “COVID-19 (Coronavirus) Guidance - Start and End Dates by Region for Sensitivity Analyses” Version 1.0 released on May 19, 2020. As of the time of finalization of this SAP, the start (and end) dates are listed below:

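### The treatment-emergent AE window ends at visits, not at last dose, and for early stoppers the documents conflict on which visits apply: about 1 to 2 months off drug, or up to about 11

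*SAP*

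**What the plan says.** **Analysis window.** SAP 2.5.1 states the primary safety endpoints as measured over treatment. It limits treatment-emergent events to those starting on or after the first day of treatment and "before EOS visit or 30 days after EOT visit, whichever comes earlier". SAP 2.8.1 repeats the end: "until EOS visit or 30 days after EOT visit, whichever comes earlier". Protocol 9.5.2.1 gives only a start rule ("events started after the first dose of study treatment or events present prior to the first dose of study treatment but increased in severity", by preferred term) and no end. The general definitions in SAP 2.1 take the date of last administration from the CRF, and SAP 2.4.1 uses it for exposure. The AE window does not use it.

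**Which visits apply to a patient who stops early.** Four places bear on this:

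- Protocol 5.6.2: "The patient should return to the clinic as soon as possible, after discontinuation of study drug, for a study treatment discontinuation visit". It then says that "the TD visit (EOT) and Week 52 (EOS) visits must be performed", so the prompt discontinuation (TD) visit is the EOT visit. Table 6-1 likewise has one shared TD/EOT column.
- Protocol Section 6, on the same patients: "the Week 48, planned End of Treatment (EOT) and Week 52 End of Study (EOS) visits must be performed".
- Protocol 5.6.1, which expressly covers early discontinuers, places EOS 4 weeks after last treatment but glosses last treatment in brackets as EOT, Week 48.
- SAP 5.1.1 also equates EOT with Week 48, and substitutes that visit's date when the last-administration date is missing.

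**Collection.** Protocol 7.1 collects AEs up to the end-of-study visit. Protocol 7.2.2 requires that every SAE occurring after consent and "until 30 days following the last administration of study treatment must be reported".

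**The concern.** For a completer, the EOT visit and the last dose nearly coincide, so the choice of anchor hardly matters. For an early stopper they can be far apart. Protocol 5.6.2 and Section 6 both keep such patients in the study to a Week 52 EOS visit, so late off-drug events will be in the database. Whether they count as treatment-emergent then depends on which visit the programmer takes as EOT.

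The primary endpoint is at stake. SAP Table 2-1 reports AEs, SAEs and AEs of special interest as crude absolute and relative frequencies. If months of off-drug time are included, the result no longer describes events over treatment. The tables listed in SAP 2.8.1 would not show this. Onset intervals are counted from first administration, with an open last category beyond 12 weeks, so they do not separate time on drug from time off drug. The exposure-adjusted tabulations planned in Protocol 9.5.2.1 are not listed in SAP 2.8.1, and SAP Section 4 does not record dropping them.

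**Working it through.** The plan gives no figure for this, so there is none to reproduce. The check is date arithmetic.

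**Inputs.** The window ends at min(EOS, EOT + 30 days), from SAP 2.5.1 and 2.8.1. Week 48 is day 336 and Week 52 is day 364. The last dose is at day L = 7 × week of last dose. The lag from last dose to TD visit is an assumption of 0 to 28 days, because the protocol says only as soon as possible. The upper value is realistic. Protocol 5.5.5 says: "Interruption of study drug for more than 28 consecutive days should lead to permanent discontinuation". A patient stopped by that rule is already about four weeks off drug at the TD visit.

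**Off-drug days counted = window end − L.**

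1. Planned completer: min(364, 336 + 30) − 336 = 28 days.
2. Protocol 5.6.1 with EOS 4 weeks after last dose: the EOS limb closes the window at 28 days.
3. Protocol 5.6.2 with EOT = TD visit and EOS = Week 52: min(364, L + lag + 30) − L. Lags of 0, 7, 14 and 28 days give 30, 37, 44 and 58 days. The week of stopping does not matter until about Week 44, where the EOS cap reduces 58 to 56.
4. Protocol Section 6 with EOT = Week 48 and EOS = Week 52: min(364, 366) − L = 364 − L.

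| Last dose | Off-drug days, Section 6 reading | Months |
|---|---|---|
| Week 4 | 336 | 11.0 |
| Week 12 | 280 | 9.2 |
| Week 24 | 196 | 6.4 |
| Week 36 | 112 | 3.7 |
| Week 44 | 56 | 1.8 |

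**Share of an arm's window (Section 6 reading).** Let a fraction f of an arm stop at Week s. Mean window per patient = (1−f)·48 + f·s + (1−f)·4 + f·(52−s) = 52 weeks, whatever f and s are. The share lying more than 30 days after last dose is f(52 − s − 4.3)/52. With an assumed s = 16, this is 3.0% at f = 5%, 6.1% at 10%, 9.1% at 15% and 15.2% at 25%. The discontinuation rates are assumptions.

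**Effect of a last-dose window on time at risk.** Under last dose + 30 days capped at EOS, a completer has 52 weeks and a Week 16 stopper has 16 + 4.3 = 20.3. The mean is 0.75 × 52 + 0.25 × 20.3 = 44.1 weeks at 25% stopping, against 0.95 × 52 + 0.05 × 20.3 = 50.4 weeks at 5%.

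**Effect on crude incidence.** Assume a constant background rate of 0.3 per patient-year and a last dose at Week 12. The chance of an event is 1 − exp(−0.3 × 114/365.25) = 8.9% over last dose + 30 days, and 1 − exp(−0.3 × 364/365.25) = 25.8% through Week 52. A completer followed to Week 52 also has 25.8%.

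**The case against.** The strongest reply is that Protocol 5.6.2 and Table 6-1 already identify the TD visit with EOT. The clause taking the earlier date then closes the window roughly a month later, and 5.6.1 may close it at 28 days. On those readings little is wrong, and this stands. The months-long window needs the Section 6 reading, or a TD visit that is long delayed or never held. But Section 6 is explicit about patients who discontinue early, and SAP 5.1.1 leans the same way, so a programmer could follow it in good faith.

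It can also be said that the analysis is descriptive, that the SAP narrowed a protocol definition with no end at all, and that Protocol 7.2.2 is a reporting rule whose next sentence refers to the last study visit. All true. Following patients beyond treatment is also a legitimate choice. It is not the one SAP 2.5.1 states, which is events over treatment.

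Four stronger conclusions might be inferred, and the documents support none of them:

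- *Background events pile up in the least tolerated arm and look like toxicity.* On the Section 6 reading every patient has the same 52-week window, so at a common background rate these events accrue equally across arms.
- *A patient stopped after a long interruption always has at least 58 off-drug days counted.* The EOS limb can close the window at 28 days under 5.6.1.
- *AEs leading to discontinuation are inflated.* An event starting after permanent discontinuation cannot have caused it.
- *Patients with neither visit have an unlimited window.* Protocol 5.6.3 stops assessments after withdrawal of consent and 7.1 ends AE collection at EOS, so there is little to misclassify.

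**Conclusion.** The point holds as a defect of definition in the primary safety analysis. The window is tied to visits, and for early stoppers the documents give conflicting visits. One SAP sentence therefore allows about 28 to 58 off-drug days (Protocol 5.6.1 or 5.6.2, assumed lag 0 to 28 days) or up to 336 days for a last dose at Week 4 (Protocol Section 6), against 28 for a planned completer.

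On the long reading, off-drug events are mixed into the AE, SAE and special-interest frequencies. The effect is dilution or blurring of a drug effect where early stopping is more common. The arm-level share of 3.0% to 15.2% of the window rests on assumed stopping rates of 5% to 25% and an assumed stop at Week 16, and applies to that reading only. No sample size, power or alpha figure changes.

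**What to change.** - In SAP 2.5.1 and 2.8.1, end the window for every patient at the date of last administration (already defined in SAP 2.1) plus 30 days, capped at the EOS visit. Early stoppers then have at most 30 off-drug days counted, and a planned completer 28.
- Present later events in a separate post-treatment listing, so that none is lost.
- Reconcile Protocol 5.6.1, 5.6.2 and Section 6 with SAP 5.1.1 on what EOT and EOS mean for a patient who stops early. Include the rule that replaces a missing last-dose date with the EOT, Week 48 date, which would otherwise carry the long window back in.
- Add to SAP 2.8.1 the exposure-adjusted AE tabulations of Protocol 9.5.2.1. They become necessary because a last-dose window makes time at risk differ by arm and lowers crude percentages where stopping is more common.

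The cost is one sentence in two SAP sections, one derivation and tables the protocol already plans; no new data are needed. The downside is that late off-drug events leave the main table and crude percentages must be read alongside the exposure-adjusted rates.

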### 2.5.2 Statistical hypothesis, model, and method of analysis

There are no pre-specified hypotheses and statistical models in this study. The methods to analyze the primary safety variables are outlined in [Table 2-1](#).

**Table 2-1 Primary variables and methods of analysis**

Variable	Method of analysis
Occurrence of adverse events	Summary table of absolute and relative frequency, overall and by preferred term
Occurrence of serious adverse events	Summary table of absolute and relative frequency, overall and by preferred term
Occurrence of adverse events resulting in discontinuation or dose reduction of study treatment	Summary table of absolute and relative frequency, overall and by preferred term
Occurrence of adverse events of special interest	Summary table of absolute and relative frequency, by type of AE as the risks are described for both tropifexor and CVC (risk definition for tropifexor are those that appear in the tropifexor IB or CVC IB, DSPP and eCRS) together with any other events identified during the course of this or other studies
Changes in vital signs	Descriptive statistics by visit
Changes in laboratory data	Descriptive statistics by visit

The statistical analysis of these variables is described in Section [2.8](#), along with the analysis of other safety variables.

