### 1.1 Study design

This study is a 48-week, randomized, double-blind, multicenter study that consists of a screening period, a treatment period starting from randomization on Day 1 and running to Week 48, and a follow up period of 4 weeks after the last dose of study treatment. The total study duration is up to 60 weeks.

The study population are adult male and female patients with histologic evidence of NASH and fibrosis (stage 2 or 3 as per NASH CRN histological score, F2/F3); see Inclusion and Exclusion criteria in the protocol for details.

At baseline, approximately 200 patients whose eligibility is confirmed will be randomized in a 1:1:1:1 ratio, resulting in approximately 50 patients randomized in each of the four arms:

**Arm A:** tropifexor 140 µg, once-daily

**Arm B:** CVC 150 mg, once-daily

**Arm C:** tropifexor 140 µg + CVC 150 mg, once-daily

**Arm D:** tropifexor 90 µg + CVC 150 mg, once-daily.

The primary analysis will be performed when all randomized patients have completed or discontinued the trial participation. No interim analyses are planned.

Due to the COVID-19 pandemic, it may not be possible for patients to return in time for the Week-48 visit to perform scheduled assessments including biopsies, and according to drug dispensing plan in Section 5.5.2 of the protocol, the Week-48 visit and associated assessments can be delayed up to approximately 12 weeks. Since the primary objective of the study is to determine if there is a safe combination between one of the chosen doses of tropifexor and 150 mg of cenicriviroc, all assessment results obtained, including those from eligible patients after Week 48, will be included in analyses as they are with no special plan to account for the treatment extension.

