**Table 1-1 Objectives and related endpoints**

Objective(s)	Endpoint(s)
Primary Objective(s)	Endpoint(s) for primary objective(s)

---

Objective(s)	Endpoint(s)
To evaluate the safety and tolerability of tropifexor + CVC in patients with NASH and fibrosis (stage 2 or 3 as per NASH CRN histological score, F2/F3) by monitoring adverse events, vital signs and laboratory values during 48 weeks of treatment as compared to monotherapy with each of tropifexor and CVC	Occurrence of adverse events, serious adverse events, adverse events resulting in discontinuation of study treatment, adverse events of special interest and changes in vital signs and laboratory values over 48 weeks of treatment
Secondary Objective(s)	Endpoint(s) for secondary objective(s)
To characterize the efficacy of tropifexor + CVC in patients with NASH with fibrosis stage F2/F3 as assessed by histological improvement after 48 weeks of treatment compared to monotherapies (tropifexor and CVC) compared to baseline biopsy	Proportion of patients who have at least a one-point improvement in fibrosis Proportion of patients with resolution of steatohepatitis

---

[figure not shown]

---

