### **Risk difference and $100(1 - \alpha)\%$ confidence interval**

For an investigational drug group with  $n_1$  patients at risk, independent from placebo with  $n_0$  patients at risk, of whom  $x_1$  and  $x_0$  experience a certain event, the risk difference is estimated as  $p_1 - p_0$  with  $p_1 = x_1/n_1$  and  $p_0 = x_0/n_0$ . Exact unconditional confidence limits for the risk difference will be obtained with SAS procedure PROC FREQ and option RISKDIFF in the TABLES statement, specifying the RISKDIFF option also in the EXACT statement. In case that exact method fails to produce valid results, asymptotic approach should be adopted. EXACT statement is not to be used in combination with multiple imputation, in which case asymptotic approach is adopted.

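### The primary objective compares combination safety with each monotherapy, but the visible primary analysis specifies per-arm summaries only, with no between-arm estimate or interval

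*SAP*

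**What the plan says.** SAP Table 1-1 states the primary objective as safety and tolerability of the combination "as compared to monotherapy with each of tropifexor and CVC". SAP 2.5.1 repeats it, referring to adverse events, vital signs and "laboratory values during treatment as compared to monotherapy with each of tropifexor and CVC". Protocol Table 2-1 words it the same way.

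On method, SAP 2.5.2 says "There are no pre-specified hypotheses and statistical models in this study". In SAP Table 2-1 the rows for adverse events, serious adverse events and adverse events leading to discontinuation or dose reduction read "Summary table of absolute and relative frequency, overall and by preferred term". The row for adverse events of special interest is also frequencies, by type of event. The vital-sign and laboratory rows read "Descriptive statistics by visit". The table refers to Section 2.8 for detail, and SAP 2.8.1 says "AEs will be summarized by presenting, for each treatment group, the number and percentage of patients having experienced". SAP 2.8.3 gives laboratory changes from baseline, shift tables and notable values by treatment group.

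SAP 2.7.2 assigns risk differences and odds ratios with 95% confidence intervals to the two secondary histology estimands. SAP 5.6 defines the odds ratio and the risk difference generically, for an investigational group of "patients at risk, independent from placebo with" a given number at risk. SAP 1.1 describes four active arms, "resulting in approximately 50 patients randomized in each of the four arms".

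**The concern.** The objective asks a between-arm question, and the trial has concurrent randomized arms to answer it. The answer has consequences: protocol 1.2 says the data will inform whether the combination is developed further, and protocol 9.8 says the aim is to find out whether a safe combination exists. Protocol 1.1 also raises a specific between-arm question. Both drugs may raise liver transaminases, so an additive effect is possible. Only a combination-versus-monotherapy contrast addresses that.

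As planned, readers must compare percentages across columns by eye. In arms of this size, similar percentages are compatible with a sizeable excess in either direction, and nothing in the planned tables shows how large an excess remains possible. The secondary objective, itself worded only as characterizing efficacy, gets an effect estimate with an interval. The primary objective does not.

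**Working it through.** **1. Is a safety contrast specified anywhere visible?**

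| Place | What is planned | Between-arm estimate? |
|---|---|---|
| SAP Table 2-1, adverse event rows | counts and percentages | no |
| SAP Table 2-1, vital-sign and laboratory rows | descriptive statistics by visit | no |
| SAP 2.8.1 | number and percentage per treatment group, onset intervals, liver and renal event frequencies | no |
| SAP 2.8.3 | change from baseline, shifts and notable values per treatment group | no |
| SAP 2.7.2 (secondary histology) | Cochran-Mantel-Haenszel test, risk differences and odds ratios with 95% intervals | yes |
| SAP 5.6, repeated measurements | model-based treatment difference with interval | generic; tied to no visible safety variable |

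**2. The plan's own safety precision figures (SAP 3.1, protocol 9.8.1).** These use a beta prior with both parameters 0.33 and one arm of 50, so with x events the posterior is Beta(0.33 + x, 0.33 + 50 − x).

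- x = 0: P(incidence ≤ 5%) = 98.7% (stated 98.7%).
- x = 1: P(incidence ≤ 5%) = 86.7% (stated 86.6%, which a prior of 1/3 gives).
- x = 10: P(incidence ≤ 20%) = 50.0% (stated about 50%).

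All three reproduce. All three concern a single arm, and SAP 3.1 contains no figure for a difference between arms.

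**3. What an interval for the difference would show.** Inputs: 193 randomized (protocol, Amendment 3 rationale). An even split is assumed: 193/4 = 48.25, so n = 48 per arm, all taken to be in the safety set. The documents give no expected event rates by arm, so rates of 10%, 30% and 50% are assumed, rounded to whole patients.

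Method: Newcombe's 95% interval, built from the Wilson limits (l, u) of each proportion:

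- Wilson limits: [p + z²/(2n) ± z·√(p(1−p)/n + z²/(4n²))] / (1 + z²/n), with z = 1.96.
- Lower limit of the difference d: d − √[(p₁−l₁)² + (u₀−p₀)²]. Upper limit: d + √[(u₁−p₁)² + (p₀−l₀)²].

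For 5/48 in both arms, p = 0.1042, l = 0.0453 and u = 0.2217. The half-width is √(0.0589² + 0.1175²) = 0.131.

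| Combination vs monotherapy | Difference (points) | 95% interval (points) |
|---|---|---|
| 5/48 vs 5/48 (about 10%) | 0 | −13.1 to 13.1 |
| 14/48 vs 14/48 (about 30%) | 0 | −17.8 to 17.8 |
| 24/48 vs 24/48 (50%) | 0 | −19.2 to 19.2 |
| 10/48 vs 5/48 (about 20% vs 10%) | 10.4 | −4.4 to 25.1 |

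With the planned 50 per arm, the equal-rate half-widths are 12.7, 17.5 and 18.9 points, so the shortfall from 200 to 193 changes little. A simple Wald interval at 48 per arm and 10% is slightly narrower: 1.96·√(2 × 0.1 × 0.9/48) = 12.0 points.

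**4. The comparator in SAP 5.6.** Both the odds-ratio and the risk-difference definitions set an investigational group against placebo. The arms are tropifexor (A), CVC (B) and two combinations (C, D). As worded, the definitions match no contrast in the trial. The contrasts that fit the objective are C−A, C−B, D−A and D−B.

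**The case against.** The strongest reply is that this was chosen openly. Both documents state that there are no hypotheses or models for the primary variables, that safety will be judged from the profile as a whole, and that the sample size rests on feasibility. SAP Table 2-1 follows protocol Table 9-1 in method, so the documents do not conflict. Four concurrent randomized arms shown side by side are a descriptive form of comparison, and a reader can compute a risk difference and interval from the reported counts. Both documents also warn that one patient is 2% of an arm. All of this stands, and it makes the point an improvement to the plan, not a defect in it. It does not count against an interval, because an interval needs no hypothesis or test.

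Redaction limits the claim as well. The visible SAP goes from 2.8.4.2 to 2.14, part of the vital-signs section is blacked out, and the sections that would call the repeated-measures model may be among the missing text. The statement therefore covers visible text only. Table 2-1, 2.8.1 and 2.8.3, which govern adverse events and laboratory data, show no redaction.

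A reader might infer that the placebo wording is why no safety contrast is estimated. The documents do not support that. The contrast is absent because 2.5 and 2.8 never ask for it. The only visible section that assigns risk differences and odds ratios is secondary efficacy, where protocol Table 9-2 names each combination against each monotherapy. The formulas are generic and the wording looks like template text.

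A reader might also infer that the report will claim comparable safety without support. No passage commits it to any such conclusion.

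**Conclusion.** The point holds as a recommended improvement. The primary objective is comparative, and in the visible text the primary analysis gives no combination-versus-monotherapy safety estimate with an interval, while the secondary endpoints get one. The gap is a missing estimate, not a missing test, and it follows from a declared descriptive approach.

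Its size: at about 48 per arm, equal observed rates of 10% to 50% would carry 95% intervals of roughly ±13 to ±19 points, and an observed 20% against 10% would run from about −4 to +25. These figures rest on an even split of 193, on everyone being in the safety set, on assumed event rates, and on Newcombe intervals; the exact limits in SAP 5.6 would differ somewhat.

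The placebo comparator in SAP 5.6 is a separate wording error. It also touches the odds-ratio and risk-difference definitions used for efficacy.

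**What to change.** In SAP Table 2-1 and 2.8.1, add the risk difference with a 95% confidence interval for C−A, C−B, D−A and D−B, for any adverse event, any serious adverse event, adverse events leading to discontinuation, and each adverse event of special interest. The exact limits already described in SAP 5.6 can be used. Label the intervals descriptive and unadjusted, with no tests.

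Optionally, add mean-change differences with 95% intervals for named key laboratory variables such as ALT and AST, from the repeated-measures model in SAP 5.6. The variables and visits must be named, because nothing visible links that model to a safety variable.

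As a separate correction, replace placebo in the SAP 5.6 odds-ratio and risk-difference definitions with the monotherapy comparator.

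The cost is SAP wording and some extra table columns, with no new data and no design change. The downside is the number of intervals: 4 contrasts × 3 overall categories = 12, plus 4 for each event of special interest. A few will exclude zero by chance, so the label must say that they are not to be read as tests.
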